5.3 Exploratory Objectives and Endpoints

1. To describe the following parameters in a confinement and/or ambulatory setting in smokers switching from mCC to THS 2.2 Menthol as compared to smokers continuing to smoke mCC and to SA:

Endpoints:

- Excretion of mutagenic material in urine: Ames Mutagenicity test (YG1024+S9) on Day 5 and Day 90 Visit in 24 hour urine.
- Subjective effect of smoking: Questionnaire of Smoking Urges (QSU-brief questionnaire); questionnaire Minnesota Nicotine Withdrawal Scale (MNWS)-Revised on Day 5 and Day 90 Visit, and nicotine dependence as assessed by the Fagerström Test for Nicotine Dependence (FTND) questionnaire score on Day 90 Visit.
- Cytochrome P450 2A6 (CYP2A6) activity: in plasma on Day 6, and on Day 90 Visit using the molar metabolic ratio of trans-3'-hydroxycotinine/cotinine.

2. To evaluate in smokers switching from mCC to THS 2.2 Menthol, and smokers continuing smoking mCC the relationship between NEQ and¹:

Endpoints:

- NEQ in urine by:

– Blood COHb.	– 1-NA in urine.
– MHBMA in urine.	– 2-NA in urine.
– 3-HPMA in urine.	– o-tol in urine.
– S-PMA in urine.	– CEMA in urine.
– Exhaled CO.	– HEMA in urine.
– 1-OHP in urine.	– B[a]P in urine.
– Total NNN in urine.	– HMPMA in urine.
– 4-ABP in urine.	– S-BMA in urine.
	– Total NNAL in urine.
- Selected risk markers:

– NEQ in urine by	
– hs-CRP in serum	– blood glucose in serum
– homocysteine in serum	– LDL in serum

¹ The reporting of this objective will be subject of a separate report.

– HDL in serum	– sICAM-1 in serum
– TG in serum	– WBC count in blood
– TC in serum	– Platelet count in blood
– Fibrinogen in plasma	– 8-epi-PGF2 α in urine.
– HbA1c in blood	– 11-DTX-B2 in urine.

All biomarkers measured in urine will be expressed as quantity excreted and concentration adjusted for creatinine.

3. To describe the following parameters over the course of the study in smokers switching from mCC to THS 2.2 Menthol as compared to smokers continuing smoking mCC:

Endpoints:

- The subscales from the Modified Cigarette Evaluation Questionnaire (MCEQ).
- HST questionnaire
- The following parameters measured per cigarette from the HST device.

– Total number of puffs.	– Total smoking duration.
– Total puff volume.	– Total work.
– Average puff volume.	– Average work.
– Average puff duration.	– Average pressure drop.
– Total puff duration.	– Average peak pressure drop.
– Average flow.	– Smoking intensity.
– Peak flow.	– Puffing time index.
– Total inter puff interval.	– Puff frequency.
– Average inter puff interval.	

4. To describe the following parameters over the course of the study in smokers switching from mCC to THS 2.2 Menthol:

Endpoint:

- Combustion occurrences in tobacco plugs: visual inspection of the tobacco plugs.
- Filter analysis: smoke nicotine in filter and ultra-violet (UV) absorbance at 310 nm (during confinement setting only).

5. To describe the product use over the course of the study according to the product preference of the subject.

Endpoint:

- Number of mCC or Menthol Tobacco Sticks smoked daily as reported on the usage log during the confinement period and self-reported number of any nicotine/tobacco product use on a daily basis as reported on the product use electronic diary by product preference.

5.4 Additional Endpoints

The following additional assessments will be made:

- Serology for Hepatitis B and C.
- Urine pregnancy test (females only), urine cotinine test, urine drug screen
- Alcohol breath test.
- Socio-Economic Questionnaire.
- Question on product preference.
- Chest X-ray.

5.5 Study Hypotheses And Evaluation Criteria

5.5.1 Hypotheses

The hypothesis to be tested is that the geometric mean level of the BoExp for THS 2.2 Menthol is lower relative to mCC.

For the primary analyses, the hypothesis will be tested on Day 5 for MHBMA, 3-HPMA, S-PMA, and COHb, and on Day 90 Visit for Total NNAL according to the primary and secondary objectives. For the secondary analyses, the hypothesis will be tested on Day 5, and if significant on Day 90 Visit.

5.5.2 Evaluation Criteria

The study will be considered successful if the study demonstrates a 50% reduction or more in MHBMA, 3-HPMA, S-PMA, and COHb on Day 5, and in Total NNAL at the Day 90 Visit in smokers switching from mCC to THS 2.2 Menthol as compared to smokers continuing to smoke mCC, using a one-sided test with 2.5% type I error probability.

6 INVESTIGATIONAL PLAN

6.1 Study Design

This is a randomized, controlled, open-label, 3-arm, parallel group, multi-center study. Randomization is stratified by sex and average daily mCC consumption over the last 4 weeks as reported during the Screening Visit (10 - 19 mCC/day vs. >19 mCC/day). (Figure 1).

In total, 160 eligible, healthy smoking subjects were planned to be randomized into one of the three study arms in Table 1.

**Table 1 Definition of Study Arms**

Study arm	Number of subjects
THS 2.2 Menthol	80
mCC	40
Smoking abstinence	40

However, one of the sites was closed down after a good clinical practice failure, and 160 subjects were randomized at the Tokyo Heart Centre site along with those subjects randomized at the Seisukai site prior to the site being shut down.

This is an *ad libitum* smoking study. In general, smoking/product use during the confinement period will be allowed between 06:30 AM and 11:00 PM. During the ambulatory period, there will be no smoking/product use restriction except during the three visits on site (Day 30 Visit, Day 60 Visit, and Day 90 Visit), when product use will be allowed from 08:00 AM to around 23:00 PM on Day 30, Day 60, and Day 90. Smoking/product use before 08:00 AM on Day 30, Day 60 and Day 90 are not restricted. During the second day of the Day 30 and Day 60 Visits, product use will be allowed from 06:30 AM onwards. On the second day of the Day 90 Visit, product use will be allowed after the CYP2A6 activity, MNWS and cough questionnaires and spirometry have been performed until time of discharge.

The Screening Visit will be conducted within 4 weeks prior to Admission to the investigational site (Day -30 to Day -3). Screening procedures do not necessarily have to be conducted on the same day. During the Screening Visit the study collaborator will demonstrate the use of THS 2.2 Menthol.

Prior to enrollment on Day -2, as the last procedure of the eligibility assessments, subjects will have a product test of the THS 2.2 Menthol (use of up to 3 THS Menthol Tobacco Sticks). In female subjects, the THS 2.2 Menthol product test will only be done after pregnancy is excluded by a negative urine pregnancy test. Enrollment takes place after all inclusion and exclusion criteria have been satisfactorily met. Only subjects willing and able to use the product will be enrolled in the study.

Subjects are admitted and enrolled on Day -2, but not randomized until Day 0. From Day -2 to Day 0, all subjects continue smoking their single preferred brand of mCC and baseline values will be recorded. On Day 0, subjects will be randomized to one of the 3 study arms (Table 1). Subjects will be informed of their product allocation by the study site staff on Day 1 prior to 06:30 AM.

The exposure period (from Day 1 06:30 AM until time of Discharge on Day 91) will include both the exposure in confinement and the exposure in the ambulatory setting.

The exposure period in confinement consists of 5 days of *ad libitum* use of the assigned product between 06:30 AM and 11:00 PM in THS 2.2 Menthol and mCC arms. Subjects allocated to the SA arm will be asked to abstain from smoking. Subjects have been

allowed to smoke their normal cigarettes prior to Day 1. Subjects will be provided with psychological support during the period of smoking abstinence. No medication to support SA will be allowed during the confinement period. Use of any tobacco/nicotine-containing product other than the assigned product/regimen will not be allowed and may, at the discretion of the Investigator, result in the withdrawal of the subject from the study.

On Day 6, the safety procedures will be conducted before discharge of the subject from the clinic. Use of products will be allowed on Day 6 in the THS 2.2 Menthol and mCC arms, but only after the CYP2A6 activity, MNWS and cough questionnaires and spirometry have been performed.

[figure not shown]
At the end of the confinement period (Discharge from the site on Day 6), subjects will be instructed to continue their assigned product/regimen in an ambulatory setting for 85 days. Subjects will be allowed to use nicotine replacement therapy (NRT) if considered necessary by the Investigator or requested by the subject.

Subjects will be required to make three site visits (Day 30 Visit, Day 60 Visit, and Day 90 Visit) during the ambulatory period. Each visit will cover 2 consecutive days on site. For all Visits the subject will check-in in the morning prior to 08:00 AM on the first day and will check-out on the second day.

The use of THS 2.2 Menthol will be strictly forbidden for subjects in the mCC or SA arms.

During the ambulatory period, subjects will not be withdrawn from the study for the use of nicotine/tobacco-containing products other than the assigned product/regimen. Subjects will record in a product use electronic diary any use of mCC (menthol or non-menthol), NRT, or other nicotine/tobacco-containing products on a daily basis.

After the time of Discharge on the second day of the Day 90 Visit, subjects will enter a 28-day safety follow-up period during which there will be recording of spontaneously reported new AEs/SAEs and the active follow-up of ongoing AEs/SAEs by the study site. In general, all AEs will be followed-up until resolved, stabilized (i.e., no worsening of the event), or a plausible explanation for the event has been found. The end of the study (EOS) is defined as the time of Discharge plus 28-day follow-up.

**Figure 1 Study Flowchart**

6.1.1 Timing of Confinement Period

The 9 day confinement period consists of:

- The Admission Day (Day -2).
- The run-in period is from admission on Day -2 until 06:29 AM of Day -1.
- The baseline period is from Day -1, 06:30 AM until Day 1, 06:29 AM.
- The exposure period in the confinement setting is from Day 1 06:30 AM until Day the time of Discharge on Day 6 (start of the ambulatory setting).

The exposure period in the ambulatory setting is from the time of discharge on Day 6 to the time of Discharge on the second day of the Day 90 Visit.

6.2 Selection of Study Population

6.2.1 Inclusion Criteria

The following inclusion criteria will be applicable for this study:

1. Subject has signed the informed consent form (ICF) and is able to understand the information provided in the Subject Information Sheet and ICF.
2. Subject is aged from 23 to 65 years (inclusive).
3. Subject is Japanese.

4. Smoking, healthy subject as judged by the Investigator based on all available assessments from the Screening period/Day of Admission (e.g. safety laboratory, spirometry [$FEV_1/FVC >0.7$ at post-bronchodilator spirometry, post-bronchodilator $FEV_1 >80\%$ predicted value, and post-bronchodilator FVC $>80\%$ predicted value], vital signs, physical examination, ECG, chest X-ray and medical history).
5. Subject smokes at least 10 commercially available mCCs per day (no brand restrictions) with a maximum yield of 1 mg nicotine ISO/mCC for the last 4 weeks, based on self-reporting. Furthermore, the subject has been smoking for at least the last 3 consecutive years. The smoking status will be verified based on a urinary cotinine test (cotinine ≥ 200 ng/mL).
6. The subject does not plan to quit smoking in the next 3 months.
7. The subject is ready to accept interruptions of smoking for up to 90 days.
8. The subject is ready to accept using the THS 2.2 Menthol.

6.2.2 Exclusion Criteria

The exclusion criteria are:

1. As per Investigator judgment, the subject cannot participate in the study for any reason (e.g. medical, psychiatric and/or social reason).
2. A subject who is legally incompetent, physically or mentally incapable of giving consent (e.g. emergency situation, under guardianship, prisoners or subjects who are involuntarily incarcerated).
3. The subject has medical condition requiring smoking cessation, or clinically relevant diseases (including but not limited to gastrointestinal, renal, hepatic, neurological, hematological, endocrine, oncological, urological, immunological, pulmonary and cardiovascular disease or any other medical condition [including but not limited to clinically relevant abnormal laboratory parameters]) in the judgment of the Investigator.
4. The subject has a body mass index (BMI) <18.5 or ≥ 32 kg/m².
5. As per Investigator judgment, the subject has medical conditions which require or will require in the course of the study a medical intervention (e.g. start of treatment, surgery, hospitalization) which may interfere with the study participation and/or study results.
6. The subject has used nicotine-containing products other than commercially available mCC (either tobacco-based products or NRT) as well as electronic cigarettes and similar devices, within 4 weeks prior to assessment.
7. The subject has received medication (prescription or over the counter) within 14 days or within 5 half-lives of the drug (whichever is longer) prior to the Admission Day (Day -2) which has an impact on CYP1A2 or CYP2A6 activity.
8. If a subject has received any medication (prescribed or over the counter) within 14 days prior to Screening or prior to the Admission Day (Day -2), it will be decided at the discretion of the Investigator if these can potentially interfere with the study objectives and subject's safety.

9. Concomitant use of nonsteroidal anti-inflammatory drugs (NSAIDS) or acetylsalicylic acid.
10. The subject has a positive alcohol test and/or the subject has a history of alcohol abuse that could interfere with the subject's participation in the study.
11. The subject has a positive urine drug test.
12. Positive serology test for human immunodeficiency virus (HIV) 1/2, hepatitis B or hepatitis C.
13. Donation or receipt of whole blood or blood products within 3 months prior to Admission.
14. The subject is a current or former employee of the tobacco industry or of their first-degree relatives (parent, sibling or child).
15. The subject is an employee of the investigational site or any other parties involved in the study or of their first-degree relatives (parent, sibling or child).
16. The subject has participated in a clinical study within 3 months prior to the Screening Visit.
17. The subject has previously participated in the same study at a different time (i.e. each subject can be included in the study population only once).
18. For women only: Subject is pregnant (does not have negative pregnancy tests at Screening and at Admission), or is breast feeding.
19. For women only: Subject does not agree to use an acceptable method of contraception*.

* Intrauterine device, intrauterine system, established use of oral/injectable/implantable/transdermal hormonal methods, barrier methods of contraception (condoms, occlusive caps) with spermicidal foam/gel/film/suppository, vasectomized partner(s), or true abstinence (periodic abstinence and withdrawal are not effective methods) from Screening until the end of the safety follow-up period.

6.3 Product Allocation and Blinding

6.3.1 Methods of Assigning Subjects to Product Arms

Randomization will be conducted through the Interactive Web and Voice Response System (IXRS).

Subjects will be randomized to one of the 3 arms. Each sex and each of the current mCC consumption levels (10 to 19 mCC/day and >19 mCC/day) will have a quota applied to ensure they represent at least 40% of the total study population.

Four separate randomization lists were provided (male smokers who smoke 10-19 mCC/day, female smokers who smoke 10-19 mCC/day, male smokers who smoke >19 mCC/day, and female smokers who smoke >19 mCC/day). Block randomization was used within each stratum (i.e., each list) in a 2:1:1 ratio (THS 2.2 Menthol:mCC:SA).

The randomization scheme will be generated by a statistical division within [REDACTED] and none of the study team (Sponsor and [REDACTED] investigators and study subjects will be exposed to the live randomization codes prior to randomization.

6.3.2 Blinding

This is an open-label study; therefore, the subjects and investigators will be unblinded to subject's product assignment after randomization. However, there will be a limited degree of blinding during the conduct of the study including the data review and data analysis process. In particular, PMI and [REDACTED] personnel will be blinded to the randomized product as summarized in the following table (Table 2: Blinding Scheme):

Table 2: Blinding Scheme

Blinded Study Personnel	End of Blinding Period
PMI and [REDACTED] study statisticians	After the SAP finalization or database lock ¹ , whichever comes last.
PMI study data managers	After the finalization of PMI blind database review ¹ .
PMI safety and clinical scientist	After the finalization of PMI blind database review ¹ . Can be actively un-blinded before that time point in case of the occurrence of any safety question, when appropriate.

¹ As part of the PMI Quality Control (QC) activity, data listings will be reviewed by [REDACTED] and PMI before database lock, with no access to the randomization information. Full details will be available in the data review plan.

The study scientist will be unblinded for the data review meeting, therefore the role of blinded reviewer is delegated. Any PMI and [REDACTED] personnel who are not listed in the above table will be unblinded by default.

No data will be made available from the unblinded study team to blinded study team without a dummy randomization or masking in place, and any communications among the two groups will avoid the use of subject randomization information until database lock. PMI will receive blinded data for the pre-analysis data review as planned in the data review plan.

6.3.3 Compliance to Product Allocation

During the confinement period, compliance to product/regimen allocation (exclusive use of THS 2.2 Menthol and mCC in THS 2.2 Menthol and mCC arms, respectively, and full abstinence from smoking in the SA arm) will be ensured by strict distribution of each Tobacco Stick/mCC when requested by the subject. During the ambulatory period, the subjects randomized to the THS 2.2 Menthol arm will be instructed to exclusively use THS 2.2 Menthol and subjects randomized to the SA arm will be instructed to abstain from smoking.

In addition, in subjects in the SA arm, the compliance will be chemically verified in confinement using exhaled CO breath. The cut-off point for the CO breath test value to distinguish CC use vs. no CC use will be 10 ppm (Benowitz et al. 2002). No subjects

from the SA arm will be withdrawn from the study if their exhaled CO breath test results are >10 ppm.

6.3.3.1 Dual-use

[figure not shown]
Although subjects are being requested to use solely the product/regimen allocated to them in their respective study arm, it is considered that during the ambulatory period not all subjects randomized to the THS 2.2 Menthol and SA arms might be exclusively using THS 2.2 Menthol or being abstinent at all times during the study. Subjects may concomitantly use THS 2.2 Menthol and CC (dual-use) or smoke some CC in the SA arm.

To assess dual-use of THS 2.2 Menthol and CC, PMI has defined product use categories defined by the percentage of the reported THS 2.2 Menthol Tobacco Sticks consumption during each time period of interest. The percentage use of THS 2.2 Menthol will be calculated by:

$$\frac{100 \times \text{Total number of THS 2.2 Menthol products used}}{\text{Total number of THS 2.2 Menthol products used} + \text{Total number of CC smoked (menthol and/or non-menthol)}}$$

Product use categories are summarized in **Table 20**, and **Figure 2** presents a detailed overview of their definition.

Figure 2 – Product Use Pattern Categorization

The more granular categorization scheme will be used for the definition of the PP Set and for the description of the product use patterns observed in the study whereas the less granular scheme will be used for the presentation of other study endpoints (e.g. safety endpoints) to better understand the impact of product.

6.3.3.2 Abstinence from mCC use

In order to further optimize the assessment of BoExp and increase the comparability of the levels of BoExp between THS 2.2 Menthol and SA the confounding effects of the use of any other tobacco or nicotine containing product (other than the assigned product) needs to be controlled for. Therefore a subject will be considered abstinent based on the following categorization:

- “Abstinence”: full abstinence from tobacco or nicotine containing product use other than the assigned product, biochemically verified with CO breath test ≤ 10 ppm.
- “Predominantly abstinent”: not more than 0.5 uses of any tobacco or nicotine containing product (other than the assigned product) per day on average and no more than two uses on a single day.
- “Not abstinent”: more than 0.5 uses of any tobacco or nicotine containing product (other than the assigned product) per day on average or more than two uses on a single day.

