6.5.4 Compliance to Investigational Product

During the confinement period, compliance for all study arms will be ensured by strict dispensation of the products (product by product) and collection of used Menthol Tobacco Sticks/CC butts will be documented in appropriate log..

During the ambulatory period, subjects in the 3 study arms will capture, from the time of Discharge on Day 6 to Day 90 11:00 PM the number of product used (e.g., menthol and non-menthol CC, Menthol Tobacco Sticks, or any other tobacco /nicotine-containing products including NRT) on a daily basis in the product use electronic diary. The product use electronic diary will be supplied by Sponsor and distributed to the subjects by the study site collaborator. The product use electronic diary will serve as a compliance tool in the three arms. On Day 6, the compliance to the product will be ensured by the merge of the

accountability log (from 06:30 AM to time of discharge) and the product use electronic diary. In case of discrepancy between the log and the electronic diary entries, the electronic diary entries will be considered as source of data.

In addition, in the SA arm, compliance will be chemically verified using an exhaled CO breath test during both the confinement and ambulatory periods. The cut-off point for the CO breath test value to distinguish mCC use versus no mCC use will be 10 ppm (Benowitz et al., 2002).

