**Table 16: Definition of Major Protocol Deviations**

Category	Description
Mis-randomization	Being administered the wrong product according to the randomization schedule.
Product compliance	Confinement: Use of any nicotine or tobacco-containing product other than the assigned product, using the product distribution log. Exhaled CO breath test >10 ppm for subjects from the SA arm starting from Day 2. Ambulatory: Non compliance in the THS 2.2 Menthol and SA arms will be defined for each period. Non compliance is based on product use reported in the product use Diary for Periods 2 - 4, as any of the following occurrence: - Use of more than 2 CC in a single day during the period. - Average product use from Day 1 through the end of the period is more than 0.5 CC per day.
Violation	Violation of inclusion/exclusion criteria.
Duration of 24 hour collection	Start and end times not within the 30 min window.

Among the violation of inclusion/exclusion criteria, only violations of inclusion criteria 1, 2, 4, 5 or of the exclusion criteria 2, 18 will be interpreted as impacting evaluability and lead to exclusion from the PP Set. Any violations of other inclusion or exclusion criteria will be assessed for their impact on the PP Set and evaluated during the pre-analysis data review meeting.

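### SAP 6.3.3.2: an SA subject who reports no use but has exhaled CO above 10 ppm is labelled *Predominantly abstinent* on a count that the CO result contradicts

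*SAP*

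**What the plan says.** SAP 6.3.3.2 defines three categories:

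- *Abstinence*: no use of any tobacco or nicotine product other than the assigned one, "biochemically verified with CO breath test ≤ 10 ppm".
- *Predominantly abstinent* has two count limits. The average limit is "not more than 0.5 uses of any tobacco or nicotine containing product (other than the assigned product) per day on average"; a second limit caps any one day at two uses. There is no CO term and no requirement that some use was reported.
- *Not abstinent*: more than 0.5 uses "per day on average or more than two uses on a single day". Again there is no CO term.

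SAP 6.3.3 gives the CO limit its meaning: "The cut-off point for the CO breath test value to distinguish CC use vs. no CC use will be 10 ppm". It places this verification in one setting: "the compliance will be chemically verified in confinement using exhaled CO breath". Protocol 6.5.4 is wider: "compliance will be chemically verified using an exhaled CO breath test during both the confinement and ambulatory periods". Protocol 7.5.1.1 schedules the breath test four times a day from Day -1 to Day 5, once on Day 6, and once at each of the Day 30, 60 and 90 Visits irrespective of the time of product use.

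SAP Table 16 uses CO in confinement, where a major deviation includes "Exhaled CO breath test >10 ppm for subjects from the SA arm starting from Day 2". In the ambulatory periods it does not: "Non compliance is based on product use reported in the product use Diary for Periods 2 - 4".

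Table 20 lists the three categories as the SA product use categories. They feed the product-use tables (SAP 12.5), the SA compliance summaries (SAP 12.4) and the ambulatory adverse event tables by category (SAP 12.6.4.2). SAP 10.4 admits to the compliant population SA subjects who are abstinent as defined in 6.3.3.2.

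**The concern.** The CO test is there to check the self-report. When it fails for someone reporting zero use, the plan's own cut-off says that the zero is wrong. The rule then tests that same zero against the 0.5-per-day and two-per-day limits, and it passes. The subject is shown as a limited user although no reliable count supports that.

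This matters most in the ambulatory period. There the 6.3.3.2 category is the only SA classification in which CO plays any part, because Table 16 compliance for Periods 2 to 4 rests on the diary. At stake is how the SA reference arm is described: the *Predominantly abstinent* row, and the adverse event column under that label, may include subjects whose actual use is unknown and may exceed the limits.

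**Working it through.** The plan gives no figure to reproduce, since this is a classification rule. The check applies the text literally.

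**Inputs.** From SAP 6.3.3.2: *Abstinence* if use = 0 and CO ≤ 10; *Predominantly abstinent* if mean ≤ 0.5 and maximum ≤ 2; *Not abstinent* if mean > 0.5 or maximum > 2. From Table 16: non-compliant in confinement if any other product is used or CO > 10 (SA arm, from Day 2); non-compliant in the ambulatory periods if more than 2 cigarettes on a day or a mean above 0.5 per day. Uses are taken to be cigarettes.

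| Mean/day | Max/day | CO (ppm) | 6.3.3.2 criteria met | Table 16, confinement | Table 16, ambulatory |
|---|---|---|---|---|---|
| 0 | 0 | 10 | *Abstinence* and *Predominantly* | compliant | compliant |
| 0 | 0 | 11 | *Predominantly* only | non-compliant | compliant |
| 0 | 0 | 40 | *Predominantly* only | non-compliant | compliant |
| 0.1 | 1 | 5 or 40 | *Predominantly* only | non-compliant | compliant |
| 0.5 | 2 | 5 or 40 | *Predominantly* only | non-compliant | compliant |
| 0.1 | 3 | 5 or 40 | *Not abstinent* | non-compliant | non-compliant |
| 0.6 | 2 | 5 or 40 | *Not abstinent* | non-compliant | non-compliant |

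**What follows.**

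1. CO never decides between the two lower categories. For a zero-use reporter, any reading above 10 ppm costs exactly one step.
2. A zero-use subject with CO at or below 10 ppm meets the criteria of both upper categories, so the rule needs a stated order of assignment.
3. In the ambulatory columns the zero-use subject with CO of 40 ppm is compliant, so no other SA rule picks up the discrepancy.

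**After the change.** Only the two rows with zero use and CO of 11 or 40 ppm move, from *Predominantly abstinent* to *Not abstinent*. All other rows keep their label.

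**The case against.** The best defence is that 10 ppm separates use from no use. It does not separate light use from heavier use. A reading above it refutes a claim of zero, but not limited use, which is what *Predominantly abstinent* describes, so dropping one step is coherent. The SAP revision history ties CO verification to the full-abstinence category, which suggests that the placement was deliberate. An ambulatory CO value is also one spot reading.

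For subjects who report some use within the limits, this defence stands in full: their CO agrees with their diary and their label is right. For zero-use reporters it stands only in part. CO shows that use was not zero, but nothing shows that it stayed within the limits, because the only count available is the one just refuted. The documents do not say that *Not abstinent* is the intended label. It is the cautious choice, and SAP 12.1.5 makes a similar one for non-safety summaries when the diary is too sparse, by counting missing days at the baseline cigarette use.

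A reader might infer more than the documents support:

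- *That every SA subject with CO above 10 ppm and reported use at or below 0.5 per day is misplaced.* Only zero-use reporters have a contradicted count.
- *That Tables 16 and 20 contradict each other in confinement.* One honestly logged cigarette over five days gives 1/5 = 0.2 per day with a maximum of 1. That is also a major deviation and also *Predominantly abstinent*. The two rules serve different purposes.
- *That abstinence is overstated in the top row.* The CO condition already removes these subjects from *Abstinence*, and Table 20 shows *Predominantly abstinent* separately.
- *That per-protocol membership or the primary result is affected.* Table 16 does not use these categories, and the primary analysis compares THS 2.2 Menthol with mCC.

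There is also containment. SAP 12.4 summarises SA-arm CO by product use category, with a confinement table, so the mismatch is visible there. The adverse event tables by category supplement those by randomization arm.

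**Conclusion.** The point holds for zero-use reporters with CO above 10 ppm, and for no one else. Their label rests on a count that the plan's own cut-off rejects.

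It is a modest defect. It touches the descriptive SA-arm product-use and compliance tables and the supplementary ambulatory adverse event tables by category. It reaches the SA part of the compliant population, and so the THS 2.2 Menthol versus SA sensitivity comparisons, only if abstinent in SAP 10.4 is taken to include *Predominantly abstinent*. Sample size, power and type I error do not change.

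The documents give no basis for estimating how many subjects are involved. It could be none, and the planned SA arm of about 40 in the full analysis set is only an outer bound for tables on that set. The conclusion rests on two assumptions: that SAP 6.3.3's reading of 10 ppm is accepted, and that ambulatory CO results may be used for verification, as Protocol 6.5.4 states and SAP 6.3.3 leaves out.

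**What to change.** In SAP 6.3.3.2 and Table 20, before database lock:

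1. State the order of assignment, so that zero use with CO at or below 10 ppm goes to *Abstinence* and is not also eligible for the next category.
2. Classify zero reported use with any scheduled CO above 10 ppm in the period as *Not abstinent*, because the reported count cannot be relied on. In confinement this uses tests from Day 2 onward. In the ambulatory periods it uses the Day 30, 60 and 90 tests, consistent with Protocol 6.5.4. Where the category covers the whole ambulatory period, as in the adverse event tables, all three tests count.
3. State that subjects reporting use within both limits keep *Predominantly abstinent* whatever their CO.

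SAP 6.3.3 should be aligned with Protocol 6.5.4 on the setting of CO verification.

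The cost is one clause and a small change to the derivation; the CO data are already collected. The downside is that in the ambulatory periods one spot reading can override about a month of diary data for a zero-use reporter, so fewer SA subjects may be counted as *Predominantly abstinent*.
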